#### ***PRN medications will be permitted***

In addition to the medications taken regularly each day, subjects will be permitted to continue to use PRN pain medications as needed. Subjects who are not using opioids during baseline will be permitted to use any non-opioid medications as prescribed by their physician in addition to over-the-counter medications (e.g., acetaminophen, ibuprofen, etc.) as PRN medications affecting

pain as needed. Subjects who are using opioids during baseline will also be permitted to increase their use of their existing opioid as prescribed by the investigator.

Subjects will also be permitted to use over-the-counter medications as needed for pain (e.g., headache or back pain) unrelated to their post-amputation pain.

PRN medication use will be documented in the diary.

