- Depression (Beck Depression Inventory (BDI-II)) at monthly intervals after start of therapy

The analysis of treatment effect on depression examines the statistical superiority of the mean percent improvement from baseline at monthly intervals of Group #1 relative to that of Group #2. In Group #1, the baseline BDI-II score (assessed at Visit 1) will be compared to the BDI-II score at each monthly interval after start of therapy. In Group #2, the baseline BDI-II score will be compared to the score at the end of the 4-week sham period. The null hypothesis is that there is no difference in mean percent improvement between the two treatment groups (*i.e.*, Group #1 at the monthly interval vs. Group #2 at end of sham period), versus the alternative hypothesis, that the mean percent improvements differ from one another. Testing will be conducted at the 0.05 level of significance.

- Analgesic usage

The analysis of treatment effect on analgesic usage will evaluate the change in opioid analgesic usage separately from the change in non-opioid analgesic usage (see Exploratory Measures, Section 9.4).

Changes in opioid analgesic usage will be calculated using morphine equivalent dosing (MED) to compare the mean percent change from baseline to the end of first 4 weeks in Group #1 relative to that of Group #2. Analysis will be conducted to determine if the mean change of Group #1 is statistically significantly greater than the mean improvement of the Group #2. The change in the opioid analgesic usage will be determined for subjects (who are receiving prescribed opioid medications at baseline) by taking the mean of the daily MED for the entries reported in the 7-day diary at baseline compared to the mean of the daily MED for the entries reported in the 7-day diary during the week before Visit 7 (*i.e.*, week 4 of home trial). The null hypothesis is that the mean change in MED is not significantly different in both groups, and the alternative hypothesis is that the mean change for the two groups differ.

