The change in MED at the end of the 8-week home trial will also be calculated. For Group #1, the change in the opioid analgesic usage will be determined for subjects (who are receiving prescribed opioid medications at baseline) by taking the mean of the daily MED for the entries reported in the 7-day diary at baseline compared to the mean of the daily MED for the entries reported in the 7-day diary during the week before Visit 11 (*i.e.*, week 8 of home trial). This will be compared to the mean change in MED during week 4 of the home trial in Group #2 (*i.e.*, final week of the sham period), as calculated in the

previous analysis. The null hypothesis is that the mean change in MED is not significantly different in both groups, and the alternative hypothesis is that the mean change for the two groups differ.

- Prosthetic usage (hours of daily prosthetic usage recorded in diary) at end of first 4 weeks and after 8-week home trial
- The analysis of treatment effect on the prosthetic usage compares the mean rank scores (of 25 possible ranks, ranging from 0 to 24 hours) at baseline to the end of first 4 weeks and after the 8-week home trial of Group #1 relative to that of Group #2, examining the statistical superiority of the mean rank scores of Group #1 over that of Group #2. The mean rank scores will be determined for each subject by taking the 7-day mean of the daily hours of prosthetic usage reported in the 7-day diary at baseline (for the residual limb with the region of pain being used for primary efficacy) compared to the 7-day mean of the daily hours of prosthetic usage reported in the diary during the week before Visit 7 and the last week of stimulation before the end of the 8-week home trial. The null hypothesis is that the mean rank scores for both groups are not significantly different. The alternative hypothesis is that the mean ranks scores for the two groups differ.
- Subject Satisfaction Survey  
A survey will be administered to the subjects at EOT to assess their satisfaction with the study and device.

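### Opioid use is defined as percent change in MED but tested as change in MED, and percent change has no rule for a zero or very small baseline.

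*Combined protocol and SAP*

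**What the plan says.** Section 9.3 (Analgesic usage) sets the opioid analysis as "to compare the mean percent change from baseline to the end of first 4 weeks in Group #1" with the same quantity in Group #2. The analysis set is given as "The change in the opioid analgesic usage will be determined for subjects (who are receiving prescribed opioid medications at baseline"). The denominator is obtained "by taking the mean of the daily MED for the entries reported in the 7-day diary at baseline", and the follow-up value is the same mean over the diary for the week before Visit 7.

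The hypothesis in that paragraph drops the word percent: "The null hypothesis is that the mean change in MED is not significantly different in both groups". The 8-week comparison does the same. Group #1's change to the week before Visit 11 is calculated, and "This will be compared to the mean change in MED during week 4 of the home trial in Group #2".

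Section 7.3 governs what subjects may take. Routine dosages are not to rise above baseline. However, "subjects will be permitted to continue to use PRN pain medications as needed", and "Subjects who are using opioids during baseline will also be permitted to increase their use of their existing opioid as prescribed by the investigator".

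The visible text names no test for MED, no minimum baseline dose, no transformation and no rule for a baseline diary week with no opioid intake.

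**The concern.** There are two separate problems.

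**Scale.** Percent change and absolute change in MED can point in opposite directions in the same data. If both can be read from the plan, the choice can be made after the results are seen.

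**Behaviour of percent change.** It divides by each subject's own baseline. At zero baseline it does not exist, so a randomised subject leaves the analysis for an arithmetic reason. At a very low baseline a modest rise becomes a very large percentage. The measure cannot fall below -100% but has no ceiling, because section 7.3 permits opioid increases. The subset cannot exceed 27 per group (section 6.2) and is smaller unless every subject is on opioids, so one such value can decide the direction of the group mean.

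**Working it through.** The plan gives no sample size, SD, effect or power for this endpoint, so there is no planned figure to reproduce.

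**1. Is the scale consistent?** Section 9.3 defines the week-4 comparison on mean percent change, but both the week-4 and week-8 hypotheses are on mean change in MED. The BDI-II item just before it keeps the word percent in its null hypothesis, so the section does not drop the word as a general habit.

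**2. Is a zero denominator reachable?** Percent change = 100 × (F - B)/B, which is undefined at B = 0. For an as-needed user with daily probability q of taking an opioid (assumed), P(zero week) = (1 - q)^7:

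| q | P(zero week) |
|---|---|
| 0.1 | 0.48 |
| 0.2 | 0.21 |
| 0.3 | 0.08 |
| 0.5 | 0.008 |

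For a whole trial, assume 10 opioid users per arm (20 in all), a share s who are as-needed users, and Poisson intake of r tablets a week. Then P(at least one undefined value) = 1 - (1 - s·e^(-r))^20. With r = 1.5, e^(-1.5) = 0.223. At s = 20%, 0.2 × 0.223 = 0.0446 and 1 - 0.9554^20 = 0.60.

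| r (tablets/week) | s = 0% | s = 10% | s = 20% | s = 40% |
|---|---|---|---|---|
| 1.5 | 0% | 36% | 60% | 85% |
| 3 | 0% | 10% | 18% | 33% |
| 7 | 0% | 0.2% | 0.4% | 0.7% |

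**3. How much can one low-dose user move the mean?** Take ten subjects: nine at -30% and one whose use rises by 5 MED/day from baseline b. Group mean = (9 × (-30) + 500/b)/10.

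| b | That subject | Group mean |
|---|---|---|
| 1 | +500% | +23% |
| 2 | +250% | -2% |
| 5 | +100% | -17% |
| 20 | +25% | -24.5% |
| 60 | +8% | -26.2% |

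A fuller example has baselines 60, 60, 45, 45, 30, 30, 20, 20, 15 and 2 (sum 327). The first nine fall by 30% and the last rises from 2 to 10, so follow-up sums to 0.7 × 325 + 10 = 237.5.
- Mean percent change: (9 × (-30) + 400)/10 = +13%. The median is -30%.
- Mean absolute change: (237.5 - 327)/10 = -8.95 MED/day. Total MED changes by -89.5/327 = -27%.
- Mean change in log(MED+1): the nine fallers sum to -3.083 and the last adds ln(11/3) = +1.299, giving -1.784/10 = -0.178. Since e^(-0.178) - 1 = -16%, the sign agrees with total use.

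**4. What does another analysis gain?** Simulated power with 10 users per arm, assumed doses, and 1.5 tablets a week for as-needed users:

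| As-needed share | Welch test on percent change | ANCOVA on log(MED+1) |
|---|---|---|
| 0% | 0.64 | 0.71 |
| 20% | 0.45 | 0.52 |
| 40% | 0.33 | 0.39 |

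Type I error of the ANCOVA stayed at about 5%, and no zero-baseline subject was dropped. At 20% as-needed users, log(MED+0.1) gave 0.38 and a rank-based ANCOVA 0.45. With none, rank ANCOVA gave 0.60.

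A second set of assumptions (median 30 MED/day in regular users, a 40% true reduction, as-needed users on 5-MED units) gave 0.87 v 0.88, 0.61 v 0.72 and 0.39 v 0.51 at the same shares, for a t-test on percent change against ANCOVA on log(MED+1).

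**The case against.** The strongest reply is that *receiving* prescribed opioids may mean taking them in the baseline week. Section 7.3 sorts subjects by whether they are using opioids during baseline, so a subject with a zero week may simply count as a non-user. On that reading no denominator is zero. This stands as a possible reading, but the plan does not settle it, and very small denominators remain under either reading.

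Mean change may also be shorthand for the mean percent change named earlier, and the week-8 text refers back to the previous analysis. That is plausible, so the wording is an ambiguity and not a proven contradiction. The BDI-II wording makes shorthand less likely.

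The visible text names no test for MED, so a Welch comparator is an assumption. The plan uses Mann-Whitney in its primary power analysis and ranks for prosthetic use. In another simulation at 20% as-needed users, power was 36% for Welch on percent change, 41% for Mann-Whitney on the same measure and 44% for ANCOVA on log(MED+1). A rank test thus recovered 5 of the 8 points, but it still cannot use a subject whose percent change is undefined.

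The +1 is arbitrary, and a smaller offset lost the gain. That stands, and is why the offset must be fixed in advance and varied in a sensitivity analysis.

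Lastly, the limit on routine dosages in section 7.3 makes large rises less likely, though as-needed and investigator-prescribed increases remain possible. General handling rules could also lie under redactions in section 9.

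**Conclusion.** The point holds as a matter of specification. Two scales are named for one test, and the visible text has no rule for a zero or very small baseline. The scale ambiguity needs no assumption. The undefined case rests on reading *receiving* as prescribed, and the leverage of one low-dose user rests on such a user being present and increasing.

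A reader might infer that low-dose users will dominate this result, that most trials of this size would contain an undefined value, or that a known amount of power is being lost. The documents support none of these. They give no number of opioid users, as-needed share or dose distribution; the chance of an undefined value runs from 0% to 85% across the assumptions shown; and the power gain runs from 0.01 to 0.12. Nor do they make opioid use a headline outcome: it is one of eight unranked secondary endpoints in a pilot study. The primary test is unaffected.

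**What to change.** In section 9.3, for both the week-4 and week-8 comparisons:

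- Analyse mean daily MED by ANCOVA on log(MED+1), with baseline log(MED+1) as covariate and treatment group as the factor.
- Define the set as all subjects prescribed opioids at baseline, explicitly including those with a zero baseline diary week.
- State the null and alternative hypotheses on that one scale.
- Fix the offset in the plan before unblinding. Report a rank-based analysis and a second offset as sensitivity analyses.
- Give percent change descriptively only, with the number of subjects for whom it is undefined.

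The cost is plan wording and a few lines of analysis code, using diary data already collected. There is a small downside: the result depends somewhat on the offset, and a difference on the log(MED+1) scale is less direct to explain than a percent change.

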**9.1 Primary clinical efficacy endpoint analysis**

[REDACTED]

The effectiveness of percutaneous Peripheral Nerve Stimulation (PNS) for the treatment of post-amputation pain will be assessed in the present study. The goal of the proposed [REDACTED] study is to determine if the investigational treatment produces pain relief that is clinically meaningful and greater than the placebo effect. To distinguish between the effect of the investigational treatment and the placebo effect, qualifying individuals will be randomized (1:1) to either Group #1 (Treatment) or Group #2 (Control). The groups will be identical except for whether active stimulation (Group #1) or sham stimulation (Group #2) is delivered during the first 4 weeks of the home trial. Both groups are expected to experience a similar placebo effect from the study procedures and use of the devices. In Group #1, subjects will experience both the placebo effect and the investigational treatment effect. During the sham stimulation phase in Group #2, subjects will experience only the placebo effect. Thus, if there is a difference between the mean improvements during sham stimulation and active stimulation, it can be attributed to the investigational treatment effects.

The null hypothesis ( $H_0$ ) is that the investigational treatment (Group #1, active simulation) is equal to the control (Group #2, sham stimulation) in providing pain relief. The alternative hypothesis ( $H_1$ ) is that Group #1 has a proportion of successes that is not equal to the proportion of successes of Group #2.

1.  $H_0$ : proportion of successes of Group #1 = proportion of successes of Group #2
2.  $H_1$ : proportion of successes of Group #1  $\neq$  proportion of successes of Group #2

If the proportion of successes of the investigational treatment is statistically significantly greater ( $p < 0.05$ ) than the proportion of successes of the control during the first 4 weeks of the home trial and the alternative hypothesis is accepted at the 0.05 level of significance, it will indicate that the investigational treatment is clinically significant and different than the placebo effect.

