### 9.3 Secondary clinical efficacy endpoint analysis

Additional endpoints below will be assessed to document further the effectiveness of using the SPRINT Peripheral Nerve Stimulation (PNS) System for the symptomatic relief and management of post-amputation pain.

- Durability of the treatment effect on average pain intensity (Primary Endpoint) after 8-week home trial

The durability of the treatment effect on average pain intensity compares the proportion of subjects who successfully achieve  $\geq 50\%$  reduction from baseline in Group #1 at end of 8-week home trial relative to that in Group #2 at end of 4-week sham period, examining the statistical superiority of the proportion of successes of Group #1 over the proportion of successes of Group #2. The post-amputation pain intensity scores will be determined for each subject by applying the same method used for the primary endpoint: taking the mean of the daily average pain intensity (BPI-SF Question #5) reported in the 7-day diary at baseline compared to the mean score for the same region(s) of pain reported over the 8 weeks of treatment (*i.e.*, the average of all scores in the diaries during this period) for Group #1. To be

considered a success, subjects must have  $\geq 50\%$  reduction in all qualifying regions of pain, defined as regions of RLP and PLP with a baseline pain score  $\geq 4$  that received blinded treatment. The proportion of successes in Group #1 will be compared to the proportion of successes in Group #2 during the sham stimulation phase (Weeks 1-4 of the home trial). The null hypothesis is that there is no difference in success rates between the two treatment groups, versus the alternative hypothesis, that the success rates differ from one another.

- Durability of the treatment effect on average pain intensity (Primary Endpoint) at monthly intervals after start of therapy (3 - 12 months after start)

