#### 9.4 Exploratory endpoint analysis

Exploratory endpoints will be analyzed to provide information on additional outcome measures and how the system and subject characteristics affect the outcome of the investigative treatment on post-amputation pain. For all endpoints, data will be collected as described in the Schedule of Procedures (Appendix A).

- Treatment effect in Group #2  
Group #2 will receive stimulation during the second half of the home trial (Weeks 5-8), and the proportion of successes and/or mean improvements in outcome measures during this phase will be compared to those during the sham stimulation phase. In addition, a repeated measures analysis may be conducted to determine the within-subjects improvement from sham to stimulation.

Global impression of change (Patient Global Impression of Change (PGIC))

Analyses of changes in average RLP

[REDACTED]

Analyses of changes in average PLP [REDACTED]

Analyses of changes in worst RLP [REDACTED]

Analyses of changes in worst PLP [REDACTED]

[REDACTED]

- Non-opioid medication usage

[REDACTED]

- Pain Catastrophizing Scale (PCS)

[REDACTED]

- Clinician Satisfaction Survey

[REDACTED]

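### As worded, the week-8 prosthetic-usage superiority test compares longer with shorter active stimulation, not stimulation with sham

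*Combined protocol and SAP*

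**What the plan says.** The prosthetic-usage item in Section 9.3 is presented as an analysis of treatment effect. It examines superiority of Group #1 in mean rank scores from baseline "to the end of first 4 weeks and after the 8-week home trial of Group #1 relative to that of Group #2". One scoring rule covers everyone: "The mean rank scores will be determined for each subject by taking the 7-day mean of the daily hours of prosthetic usage" at baseline, set against the diary means "during the week before Visit 7 and the last week of stimulation before the end of the 8-week home trial". No separate window is given for Group #2. The hypotheses are two-sided: "The alternative hypothesis is that the mean ranks scores for the two groups differ".

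Section 9.1 states that the groups are identical except for "whether active stimulation (Group #1) or sham stimulation (Group #2) is delivered during the first 4 weeks of the home trial". Section 9.4 adds that "Group #2 will receive stimulation during the second half of the home trial (Weeks 5-8").

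The neighbouring analyses in Section 9.3 handle this crossover explicitly. The 8-week pain durability analysis compares Group #1 "relative to that in Group #2 at end of 4-week sham period". For the week-8 change in opioid dose, in the item just before prosthetic usage, the text reads "This will be compared to the mean change in MED during week 4 of the home trial in Group #2".

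**The concern.** A superiority test described as measuring treatment effect needs a comparator without the treatment. At week 4 the prosthetic item has one: Group #2 is concurrent, randomised and on sham. At week 8, on the scoring rule as written, it does not, because Group #2 has been switched to the same stimulation.

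The difference then measures only the part of the effect that Group #2 has not yet gained. If prosthetic hours respond within a few weeks, an effective device could show little difference at week 8, and that null result could be misread as lack of effect. A positive result would show an advantage of longer or earlier stimulation, which is not the stated question either. An analyst following the text would produce this contrast under a treatment-effect label.

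**Working it through.** **Treatment in each window.** Section 7.5 places Visit 7 at about 4 weeks and Visit 11 (end of treatment) at about 8 weeks after initial lead placement. With Sections 9.1 and 9.4 this gives:

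| Diary window | Group #1 | Group #2 | What the contrast tests |
|---|---|---|---|
| Week before Visit 7 | active, about 4 weeks | sham, about 4 weeks | treatment against sham |
| Last week of the 8-week trial | active, about 8 weeks | active, about 4 weeks, after sham | longer against shorter stimulation |

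**Group #2 comparator in the other between-group secondary analyses that go past week 4 (Section 9.3).**

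| Analysis | Group #2 taken from |
|---|---|
| Pain durability, 8 weeks | sham period |
| Pain durability, monthly | final sham week |
| Pain interference | end of sham |
| Pain Disability Index | end of sham |
| BDI-II | end of sham |
| Opioid dose, week 8 | week 4, final sham week |
| Prosthetic usage, week 8 | not stated; one rule for each subject |

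**What each contrast estimates.** Let E1(8) be the effect on hours in Group #1 after 8 weeks of stimulation, E2(4) the effect in Group #2 after its 4 weeks, and T4 and T8 the background levels at weeks 4 and 8.

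- Week 8 as written: [T8 + E1(8)] − [T8 + E2(4)] = E1(8) − E2(4). The background cancels, but so does whatever Group #2 has gained.
- Group #1 at week 8 against Group #2 at week 4: [T8 + E1(8)] − T4 = E1(8) + (T8 − T4). The effect is kept, but any time trend is added.

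With f = E2(4)/E1(8), the contrast as written is (1 − f) times the effect against sham.

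**Size, as an illustration.** The plan states no power, effect size or time course for prosthetic hours, so there is no figure to reproduce. Its only power figure (above 90%, Section 9.1.2) belongs to the primary endpoint. Assume 80% power against sham at two-sided 5%, so that the expected z is 1.96 + 0.84 = 2.80:

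- f = 0.5: z = 1.40, power Φ(1.40 − 1.96) = Φ(−0.56) = 0.29.
- f = 0.75: z = 0.70, power Φ(0.70 − 1.96) = Φ(−1.26) = 0.10. Rejections in the opposite direction would add less than 0.01.
- f = 1: z = 0, and both tails together reject at the 5% error rate.

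**The same pattern at the planned size.** Take 27 per group (Section 6.2), an assumed rank test with relative efficiency 3/π, and an assumed standardised effect d against sham. Then s = √(27 × (3/π)/2) = 3.59, and power = Φ(d(1 − f)s − 1.96) + Φ(−d(1 − f)s − 1.96):

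| d | f = 0 | f = 0.5 | f = 0.75 | f = 1 |
|---|---|---|---|---|
| 0.5 | 44% | 15% | 7% | 5% |
| 0.8 | 82% | 30% | 11% | 5% |
| 1.0 | 95% | 44% | 15% | 5% |

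**The case against.** The strongest reply is that the sham anchor was simply left out. Every sibling analysis past week 4 uses it, one of them in the item directly before, so a reader could carry the convention over. That may well be the intent. But the item states a single scoring rule for each subject and no Group #2 exception, and an analyst following it would use week-8 diaries in both groups. The synopsis and Section 4.4 lines on prosthetic usage are partly redacted, and Appendix A is not in the public text, so they cannot settle it. On either reading the wording needs correcting.

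A second reply is that a reader would not see week 8 alone. The week-4 sham comparison stands in the same item, and Section 9.4 plans a comparison of stimulation with sham within Group #2 for outcome measures, though it does not name prosthetic hours. This stands and limits the harm.

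A reader might infer that a working device is bound to show nothing at week 8, or that the sponsor would report a null as no effect on prosthetic use. The documents support neither. They give no time course for prosthetic hours and do not say how a null week-8 result would be interpreted. The dilution would usually run toward a missed effect, not a false claim of benefit.

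**Conclusion.** The point holds as a defect in the specification of one time point of one secondary endpoint. Following the text gives an active-against-active contrast at week 8, which cannot answer whether stimulation improves prosthetic use compared with sham. It remains a randomised comparison of earlier with delayed stimulation, but it is not labelled as one.

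Its size depends on how far Group #2 catches up, which is unknown. The fall from 80% to about 29%, 10% and 5% rests on an assumed starting power and assumed catch-up of one half, three quarters and all of the effect. These figures should not be read as the power of this trial's test. Nor should the point be read as undermining the prosthetic endpoint as a whole: the week-4 comparison is a valid concurrent sham comparison, and the primary analysis is untouched. The correction is cheap and worth making.

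**What to change.** In the prosthetic-usage item of Section 9.3, name the week-4 comparison as the only between-group sham-controlled test of prosthetic hours. Report week 8 by group descriptively, or label it explicitly as a delayed-start comparison of about eight with about four weeks of stimulation. Present the within-Group #2 sham-to-active comparison from Section 9.4 alongside, and state that it includes prosthetic hours.

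If the sponsor prefers the anchor used for the other endpoints (Group #1 at week 8 against Group #2 at week 4), the text should name that window and say that the contrast mixes time with treatment.

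The cost is a few sentences of analysis-plan wording. Under the preferred option one secondary superiority test is lost. No data collection changes.

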#### 4.4 Secondary Efficacy Endpoints

Several secondary endpoints are being collected to gain a better understanding of what effect, if any, the interventions will have on each measure. We intend to evaluate these endpoints

(described below) to [REDACTED]. Refer to Section 9.3 for a detailed description of each endpoint. Changes from baseline will be evaluated as secondary efficacy endpoints for the following outcome measures:

- Durability of the treatment effect on average pain intensity [REDACTED]
- Durability of the treatment effect on average pain intensity [REDACTED]
- Pain interference (BPI-SF Question #9) [REDACTED]
- Pain disability (Pain Disability Index (PDI)) [REDACTED]
- Depression (Beck Depression Inventory (BDI-II)) [REDACTED]
- Analgesic usage [REDACTED]
- Prosthetic usage [REDACTED]
- Subject Satisfaction Survey

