**6.2 Number of subjects**

[REDACTED]

Up to 54 individuals will be enrolled as subjects and randomized to either Group #1 or Group #2 using a 1:1 randomization scheme. A total of up to 54 subjects (27 subjects per group) will undergo lead placement. [REDACTED]

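### Section 9.3 tests prosthetic usage at week 4 on mean rank scores, without saying whether these are changes, baseline-adjusted values or levels

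*Combined protocol and SAP*

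**What the plan says.** Section 4.4 introduces its list, which includes prosthetic usage, with "Changes from baseline will be evaluated as secondary efficacy endpoints for the following outcome measures".

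The prosthetic-usage paragraph of Section 9.3 makes four statements relevant to the week-4 comparison:

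- The opening says that the analysis "compares the mean rank scores (of 25 possible ranks, ranging from 0 to 24 hours) at baseline to the end of first 4 weeks".
- The superiority clause continues "examining the statistical superiority of the mean rank scores of Group #1 over that of Group #2".
- The scoring sentence begins "The mean rank scores will be determined for each subject by taking the 7-day mean of the daily hours of prosthetic usage". It takes this mean from the baseline diary and says it is "compared to the 7-day mean of the daily hours of prosthetic usage reported in the diary during the week before Visit 7".
- The null hypothesis reads "The null hypothesis is that the mean rank scores for both groups are not significantly different". The alternative says that the scores differ.

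Other endpoints in Section 9.3 name the tested quantity. For opioid use, "The null hypothesis is that the mean change in MED is not significantly different in both groups". The BDI-II hypotheses concern mean percent improvement. The pain, interference and PDI hypotheses concern success rates, with success defined as a reduction from baseline.

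On size, Section 6.2 says "A total of up to 54 subjects (27 subjects per group) will undergo lead placement".

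**The concern.** The opening and the scoring sentence bring in the baseline. The superiority clause and both hypotheses, which fix what is tested, mention neither a change nor an adjustment. The scoring sentence does not say whether the comparison of the two weeks is a difference, a ratio or a percentage, and the visible text does not say what is ranked.

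An analyst could therefore defend a rank test on week-4 hours, a rank test on the difference, a test on percentage change, or a baseline-adjusted comparison. These have different power and can disagree on significance in the same data. If the choice is left open, it may be made after the data are seen.

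**Working it through.** **1. The plan's own figure.** There is none for this endpoint. The only visible power statement (Section 9.1.2, above 90% at 5% two-sided) concerns the primary endpoint.

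**2. The wording side by side.**

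| Place | Is baseline part of the quantity? |
|---|---|
| 4.4, list introduction | Yes, as a change |
| 9.3, opening | Yes, form not stated |
| 9.3, scoring sentence | Yes, form not stated |
| 9.3, superiority clause | Not mentioned |
| 9.3, null and alternative hypotheses | Not mentioned |

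**3. The rank scale.** Whole hours from 0 to 24 give 25 values for one diary day. With whole-hour entries, seven days sum to 0 to 168 hours, so a 7-day mean can take 169 values (0/7 to 168/7). The 25-rank description fits a daily entry, not the score that is analysed.

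**4. Power under each reading.** From the documents: 27 per group. The two-sided 0.05 level is taken by analogy with the other endpoints. Assumed, because the documents give no figures: baseline mean 9 h, SD s = 4 h at both times, true gain d = 2 h (so d/s = 0.5), and correlation r between baseline and week 4 from 0.3 to 0.9.

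SD of the tested quantity, in units of s:
- week-4 level: 1
- change: √(2(1−r))
- ANCOVA residual: √(1−r²)

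Power ≈ Φ(0.5 / (SD × √(2/27)) − 1.96), with √(2/27) = 0.272.

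Example at r = 0.8:
- Level: 0.5/0.272 = 1.84, giving Φ(−0.12) = 45%.
- Change: SD = √0.4 = 0.632, 0.5/(0.632 × 0.272) = 2.91, giving Φ(0.95) = 83%.
- ANCOVA: SD = √0.36 = 0.600, 0.5/(0.600 × 0.272) = 3.06, giving Φ(1.10) = 86%.

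The simulation used Mann-Whitney tests for level and change and ordinary ANCOVA on hours, with 7-day means held within 0 to 24 h.

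| r | Level: formula / simulated | Change: formula / simulated | ANCOVA: formula / simulated |
|---|---|---|---|
| 0.3 | 45% / 41% | 34% / 33% | 49% / 47% |
| 0.5 | 45% / 41% | 45% / 41% | 56% / 54% |
| 0.7 | 45% / 41% | 66% / 62% | 73% / 70% |
| 0.8 | 45% / 41% | 83% / 79% | 87% / 84% |
| 0.9 | 45% / 41% | 98% / 98% | 99% / 99% |

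(The ANCOVA formula value at 0.8 is 86.5% before rounding.)

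**5. Why the ordering does not depend on r.** For r between 0 and 1, 1−r² is at most 1, and 1−r² = (1−r)(1+r) is at most 2(1−r). Apart from one degree of freedom, the ANCOVA variance never exceeds that of either alternative.

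**6. Sensitivity.** With mean 8 h and SD 5 h, levels give about 28% and ANCOVA 38/51/66/90% at r = 0.5/0.7/0.8/0.9. The ANCOVA advantage also held with 15% of subjects at zero hours.

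**7. Error rate and agreement.** Type I error was near 5% for every test. With SD 4 h and r from 0.5 to 0.9, the level and change tests differed on significance in 33 to 58% of simulated trials with a 2 h gain, and in 7 to 10% with no effect.

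**The case against.** The strongest reply is that the score is already defined against baseline. The scoring sentence uses the same construction that Section 9.3 uses for the opioid change and Section 9.1 for the primary pain reduction. Hypotheses elsewhere also use shorthand: the success-rate hypotheses do not repeat that success is a reduction from baseline. On that reading, 9.3 agrees with 4.4 and only the word change is missing. This largely stands. A reader might infer that the plan tests week-4 usage while ignoring baseline, but the documents do not show that.

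The 25-rank wording is a small matter by itself, because averaging does not alter which groups are compared. That also stands.

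The prosthetic entry in 4.4 runs into redacted text, as do parts of Sections 9.0 and 9.1, so a test or general method may be named there. The point therefore rests only on the visible hypotheses and scoring sentence.

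Finally, ANCOVA may be called a preference, and inserting the word change would be enough to align the text. That would remove most of the ambiguity. It would still leave difference versus percentage open, and for a difference it would give up some power at every correlation in the table. Linearity on a bounded 0 to 24 h outcome is a fair caution, and the simulation's near-normal data favour ANCOVA. A rank-based version answers most of this.

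**Conclusion.** The week-4 hypotheses for prosthetic usage leave the tested quantity undefined, and the rank scale does not match the score. A baseline-referenced score is the more natural reading; a level comparison remains possible. Adjusting for baseline hours is at least as good under either reading.

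Two stronger inferences are not supported:

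- A reader might conclude that power roughly halves. That needs both the level reading and a correlation near 0.8 (41% against 79% for change). At 0.5 there is no loss against change, and at 0.3 the level test does better (41% against 33%). The documents give no correlation.
- A reader might conclude that chance baseline imbalance invalidates the result. With 27 per group, the standard error of the baseline difference is 0.27 SD, so some imbalance is expected. Randomisation allows for it, and type I error stays near 5%. The cost is precision.

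All power figures rest on the assumed SD, gain and correlation. Severity is low: one secondary endpoint of a pilot study. The point covers the week-4 comparison only; the week-8 comparison was not assessed.

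**What to change.** In the prosthetic-usage paragraph of Section 9.3, for week 4:

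- Define the outcome as the 7-day mean of daily hours of use in the week before Visit 7.
- Compare groups by ANCOVA with the 7-day baseline mean hours as covariate. Use rank-based ANCOVA as a sensitivity analysis, or as the main analysis if the sponsor wishes to keep a rank method.
- State the null hypothesis as equal baseline-adjusted usage in the two groups and the alternative as unequal, instead of in terms of significance.
- Delete the 25-rank wording, or say that ranks are taken across subjects on the 7-day means.

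This agrees with Section 4.4, because with baseline as covariate the estimated group difference is the same whether the outcome is week-4 hours or the change in hours.

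The cost is one paragraph of text, changed before unblinding. The diary data are already collected, so no subjects or visits are added. The small downside is a linear-model assumption on a bounded outcome, which the rank-based analysis checks.
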